**Table 8: Study Events Schedule for Cohort 3 (continued)** 

Visit Activities:	Visit 1	Visits 2a-2d P	Visit 3	Visit 4	Phone Calls N	Visit 5	Visit 6	Visit 7	Phone Calls N	Visit 8	Phone Call N	Visit 9
	Screening	Plasmapheresis Collections	Infusion #1	24-Hour Follow-Up	48 & 72 hrs	7-Day Follow- Up	Infusion #2	24- Hour Follow- Up	48 & 72 hrs	7-Day Follow- Up	14-Day	28-Day Follow- Up
Study Day*:	-56 to -49	-55 to -35	1	2	3 & 4	8	15	16	17 & 18	22	29	43
Visit Window:				± 3 hrs	± 2 hrs	± 1 day	± 3 days	± 3 hrs	± 2 hrs	± 1 day	± 2 hrs	± 1 day
Visual Inspection of Blood Components		X	X				X					
FDP/FFP Infusion			X				X					
Exit Interview G												X
Laboratory Tests	•		•		•	•		•		•	•	
Urine Drug Screening	X											
Urine Pregnancy Test (females only)	X		$X^{J}$				$X^{J}$					
Urinalysis	X		$X^{J}$	X			$X^{J}$	X				
Chemistry Panel I	X		$X^{J}$	X		X	$X^{J}$	X		X		
$CBC^K$	X		$X^{J}$	X		X	$X^{J}$	X		X		X
Hematocrit		X										
PT/INR, aPTT	X		$X^{J}$	X			$X^{J}$	X				X
DAT (IgG and C3)	X		$X^{J}$	X			$X^{J}$	X				X
SPEP		$X^{L}$										
Blood Type for ABO and Rh	X		$X^{J}$				$X^{J}$					
Red-Cell Antibody Screen	X											
Syphilis Screen	X											
HTLV Antibody Screening Test	X											

**Table 8: Study Events Schedule for Cohort 3 (continued)** 

Visit Activities:	Visit 1	Visits 2a-2d P	Visit 3	Visit 4	Phone Calls N	Visit 5	Visit 6	Visit 7	Phone Calls N	Visit 8	Phone Call N	Visit 9
	Screening	Plasmapheresis Collections	Infusion #1	24-Hour Follow- Up	48 & 72 hrs	7-Day Follow- Up	Infusion #2	24- Hour Follow- Up	48 & 72 hrs	7-Day Follow- Up	14-Day	28-Day Follow- Up
Study Day*:	-56 to -49	-55 to -35	1	2	3 & 4	8	15	16	17 & 18	22	29	43
Visit Window:				± 3 hrs	± 2 hrs	± 1 day	± 3 days	±3 hrs	± 2 hrs	± 1 day	± 2 hrs	± 1 day
HIV-1/2, HBV, HCV, & West Nile Virus Nucleic Acid Tests	X											
Cross-match RBC vs. FDP/FFP			X				X					
Reverse Type of FDP/FFP			X				X					
Coagulation Factor Tests M			$X^{J}$				$X_{1}$					
D-Dimer Test	X		$X^{J}$	X			$X^{J}$	X				
Total Protein O		X					X J					
PF 1+2, TAT, AT- III, Alpha-2 Antiplasmin, and C3a des Arg Q			$X_{l}$				X J					

\*The estimated manufacturing time is 5 weeks.

<sup>AThe AABB donor history questionnaire is administered at all donation visits.

<sup>BConfirm data are accurate; subject is healthy with no significant medical history change.

<sup>C Complete physical exams to include height (screening only), weight, vital signsE, and a targeted assessment of health as described in section 7.2 and section 8.2.

<sup>DAbbreviated physical exam to include vital signs E and a general assessment of health.

<sup>EVital signs monitored are blood pressure, heart rate, respiration rate, and temperature. These will be measured every 15 minutes (± 5 minutes) during the infusion, every 30 minutes (± 5 minutes) between 0 and 4 hours post-infusion, and then every 4 hours (± 40 minutes) until the subject is released from the clinic.

<sup>FEach plasmapheresis session is to be scheduled approximately 7-10 days apart. Cohort 3 will require 3 to 4 plasma donation sessions.

<sup>GExit interview may take place at any point during the study and is dependent upon subject's continued enrollment status.

<sup>HMonitor vital signs every 15 minutes during infusion; every 30 minutes for up to 4 hours post-infusion; and after 6 hours, vital signs should be measured every 4 hours until the subject is released. Subjects assessed for DVT, PE, and cardiac ischemia using the Wells Scale prior to infusion, at 30 minutes, 4 hours, and 24 hours post-infusion before the subject can be released from the clinic.

<sup>1Chemistry panel includes Calcium, ALP, ALT, AST, Bicarbonate, Chloride, Glucose, Potassium, Sodium, Total Bilirubin, Total Protein, BUN, Lactate, and Creatinine. pH, Ionized Calcium and Total Magnesium will only be measured at pre-infusion and 0.5 hour post-infusion.

<sup>JSee Table 9 - Laboratory Testing Schedule and Volumes for Cohort 3 for sampling time points.

KCBC comprises Hematocrit, Hemoglobin, Platelet Count, RBC Count, and WBC Count.

<sup>LSPEP is performed on the donated plasma at each plasmapheresis visit.

MCoagulation testing for Factors I, II, V, VII, VIII, IX, X, XI von Willebrand Factor activity, and Total Protein C and S activity.

N Follow-up phone calls to the subject will be made 48 hours and 72 hours following both Infusion Visits. The 14-day follow-up phone call will only occur after Infusion Visit #2.

<sup>o Total Protein can be performed up to 24 hours prior to each subsequent plasmapheresis session.

PAdditional collection visits may be required in the event that a plasma unit experiences an issue during preparation (eg, leakage during transfer to lyophilization bag) or during lyophilization (eg, bag breakage during freeze-drying).

O These tests are for research purposes only and will not be used to manage the safety of study participants.

Table 9: Laboratory Testing Schedule and Volumes for Cohort 3

Laboratory and Coagulation Factor Testing	Screening	Collection Visits		fusion Visit #1 and #2	ts	24-Hour Follow-Up	7-Day Follow-Up	28-Day Follow-Up
			Pre-	Post-I	nfusion	Visits	Visits	Visit
			Infusion	0.5 hr	4 hrs			
Pregnancy Test (females only)	X		X					
Urine Drug Screening	X							
Urinalysis	X		X	X	X	X		
Chemistry Panel A	X		X	X	X	X	X	
CBC B	X		X	X	X	X	X	X
Hematocrit		X						
PT/INR	X		X	X	X	X		X
aPTT	X		X	X	X	X		X
DAT (IgG and C3)	X		X			X		X
Blood Type for ABO and Rh	X		Xc					
Red-Cell Antibody Screen	X							
Syphilis Screen	X							
HTLV Antibody Screening Test	X							
HIV-1/2, HBV, HCV, and West Nile	X							
Virus Nucleic Acid Tests								
Cross-match RBC			X					
Reverse Type FDP/FFP			X					
Coagulation Factor Tests D			X	X	X			
D-Dimer Test	X		X	XF	XF	X		
Total Protein G		X						
PF 1+2, TAT, AT-III, Alpha-2			X	X				
Antiplasmin, and C3a des Arg								
Plasma Collection		X						
$SPEP^{G}$		X						
Total Blood Volume Collected	~51mL	~607mL E	~68mL	~64mL	~58mL	~34mL	~21mL	~20 mL

<sup>AChemistry panel includes Calcium, ALP, ALT, AST, Bicarbonate, Chloride, Glucose, Potassium, Sodium, Total Bilirubin, Total Protein, BUN, Lactate, and Creatinine. pH, Ionized Calcium and Total Magnesium will only be measured at pre-infusion and 0.5 hour post-infusion.

<sup>BCBC comprises Hematocrit, Hemoglobin, Platelet Count, RBC Count, and WBC Count.

<sup>CABO only at this time point.

<sup>DCoagulation testing for Factors I, II, V, VII, VIII, IX, X, XI, von Willebrand factor activity, and Protein C and S activity.

<sup>ECollection volume for this visit includes the plasma donation volume (approximately 600 mL plasma collected at each visit).

FD-Dimer collection at 30 minutes and 4 hours post-infusion must be done STAT. Results must be received and reviewed by the PI prior to the subject's release from the clinic.

GSPEP is performed for subjects at each plasmapheresis session. Total Protein will be performed STAT or up to 24 hours prior to plasmapheresis at each subsequent plasmapheresis session.

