#### Collection Volume Limits via Plasmapheresis Collection

Donor Weight	Plasma Volume or Weight	Collection Volume*
10 – 149 lbs	625 mL (640 g)	690 mL (705 g)
150-174 lbs	750 mL (770 g)	825 mL (845 g)
≥175 lbs	800 mL (820 g)	880 mL (900 g)

\*includes anticoagulant volume

As shown in the Cohort and Treatment Arm Details table below, subjects' assigned cohorts and treatment arms indicate the type, frequency, and total volume of blood/plasma donations required. Subjects in Cohorts 1 and 2 are to provide sufficient plasma volume for a single infusion with either 1 or 2 units, respectively, and based on assigned treatment arm, they are to provide plasma through WB

or plasmapheresis collection for manufacture of autologous FDP-CPD or FDP-ACD. Cohort 2 subjects in the FDP-CPD treatment arm are required to successfully make 2 WB donations within a relatively short period of time to provide adequate volume for their use in the trial. Because of the extraordinarily long time required to accrue sufficient WB-derived plasma for the high dose cohort (approximately 11 months), the FDP-CPD treatment arm is not included in Cohort 3. The total starting volume of plasma needed from each Cohort 3 subject is approximately 1,620 mL; triple that of Cohort 2 and thus inclusion of this treatment arm in Cohort 3 would require 6 WB donations, increasing subject risk for significant iron store depletion and anemia.

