# 5.7. Route of Administration, Dosage Regimen, Treatment Period, and Justification

In this safety study, 3 cohorts of healthy subjects will receive an intravenous (IV) infusion of FDP and/or FFP as follows:

- **Cohort 1:** Eight enrolled subjects will each receive a 1 unit (approximately 270 mL) dose of FDP:
  - Arm 1 subjects will receive 1 unit (approximately 270 mL) of autologous FDP manufactured from WB. These subjects are expected to make one WB donation. Subjects with a low-volume donation (< 450 mL) may be withdrawn from the study. The site will discard the low-volume donation per their SOP for handling blood and blood products.

  - Arm 2 subjects will receive 1 unit (approximately 270 mL) of autologous FDP manufactured from plasmapheresis collected FFP. These subjects are expected to undergo one plasmapheresis session. Subjects with a low volume donation (< 500 mL) may be withdrawn from the study. The site will discard the low-volume donation per their SOP for handling blood and blood products.

- Cohort 2: Eight enrolled subjects will each receive 2 units (approximately 540 mL) of FDP:
  - Arm 3 subjects will receive 2 units (approximately 540 mL) of autologous FDP manufactured from WB. These subjects are expected to make two WB donations that are scheduled a minimum of 28-days apart. Subjects with a low-volume donation (< 450 mL) may be withdrawn from the study. The site will discard the low-volume donation per their SOP for handling blood and blood products.

  - Arm 4 subjects will receive 2 units (approximately 540 mL) of autologous FDP manufactured from plasmapheresis collected FFP. These subjects are expected to undergo one plasmapheresis session. Subjects with a low-volume donation (< 500 mL) may be withdrawn from the study. The site will discard the low-volume donation per their SOP for handling blood and blood products.
    - Should an Arm 4 subject require a second plasmapheresis collection attempt, to ensure subject safety, serum protein electrophoresis (SPEP) and STAT total protein will be performed just prior to the subsequent plasmapheresis. If any abnormalities are detected, the subject will be referred to a physician, scheduled for early withdrawal, and replaced with another subject.

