Treatment Arm 4 subjects will provide a single unit plasmapheresis donation (up to 800 mL) using the standard procedures in place at the site. Subjects will undergo SPEP, which will be measured during their plasmapheresis donation. Post-donation, subjects will be monitored for any adverse effects associated with plasmapheresis donation (see section 5.6.1.3). A second plasmapheresis donation visit should not be required for Treatment Arm 4 subjects. Subjects providing a low volume plasmapheresis donation (< 500 mL) may, at the discretion of the investigator, be withdrawn from the study or scheduled for a second donation attempt. If a subsequent visit is scheduled to collect the volume of plasma required to manufacture the 2 units (approximately 540 mL, total) of FDP, an additional visit may be scheduled no less than 7 days from the date of the first donation. SPEP and STAT Total Protein will both be performed at any subsequent collection visits as a condition of initiating plasmapheresis.

Following standard blood collection SOPs, subjects who present to a collection visit with a low hematocrit may, at the discretion of the PI, be rescheduled for a later blood/plasma collection.

All low-volume collections will be discarded by the clinical site following their SOP for handling blood and blood products.

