#### 8.1.3. Cohort 3 Plasma Collection

WB-derived plasma will not be used in Cohort 3 due to safety concerns regarding the number of donations required to collect the volume of plasma needed to manufacture 3 units (approximately 810 mL) of FDP and 3 units (approximately 810 mL) of FFP. All subjects in Cohort 3 will undergo plasmapheresis collection. Cohort 3 subjects will be randomized no more than 48 hours prior to the first infusion to 1 of 2 treatment arms that will be based on the order of the products received. Subjects in Treatment Arm 5 will receive a 3 unit (approximately 810 mL) transfusion of FDP followed by a 3 unit (approximately 810 mL) transfusion of FFP. Subjects in Treatment Arm 6 will receive a 3 unit (approximately 810 mL) transfusion of FFP followed by a 3 unit (approximately 810 mL) transfusion of FDP. Subjects will be blinded to their treatment order assignments.

During the Collection Visits, all Cohort 3 subjects will:

• Be asked to provide information about medical history, concomitant medications, and AEs since the screening visit;

- Undergo an abbreviated physical exam which includes vital signs (blood pressure, heart rate, respiration rate, and temperature) and a general assessment of health;
- Complete the AABB Donor History Questionnaire;
- Provide a sample of blood for hematocrit testing prior to (each) donation per the SOPs in place at the site; and
- Provide a plasma donation by plasmapheresis in compliance with the clinical site's SOPs regarding plasmapheresis donation.

Cohort 3 subjects will need to make 2 to 3 plasmapheresis donations (up to 800 mL per collection) that will be scheduled to take place, minimally, a week apart. Post-donation, subjects will be monitored for any adverse effects associated with plasmapheresis donation (see section 5.6.1.3). The SPEP will be routinely performed at as part of all Cohort 3 collection visits. Should the SPEP results reveal the subject as ineligible for their current plasmapheresis, the subject may be rescheduled to return in no less than 7 days. Just prior to Cohort 3 subjects' second or subsequent plasmapheresis donation at each plasmapheresis collection, a SPEP test will be performed. After the first plasmapheresis collection, a STAT Total Protein will be performed as a condition of initiating plasmapheresis at subsequent collection visits. Post-donation, all subjects will be monitored for any adverse effects associated with plasmapheresis donation (see section 5.6.1.3).

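### Table 8 footnote L runs the Cohort 3 SPEP on donated plasma, so it cannot serve as the pre-donation eligibility check that section 8.1.3 requires at repeat collections

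*Protocol*

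**What the plan says.** Four places in the Protocol bear on the Cohort 3 SPEP.

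- **Table 8, footnote L (section 6.5)** names the specimen: "SPEP is performed on the donated plasma at each plasmapheresis visit".
- **Section 8.1.3** sets the timing: "Just prior to Cohort 3 subjects' second or subsequent plasmapheresis donation at each plasmapheresis collection, a SPEP test will be performed". It also says how the result is used, for the case where "SPEP results reveal the subject as ineligible for their current plasmapheresis, the subject may be rescheduled to return in no less than 7 days". A separate test is required as well: "After the first plasmapheresis collection, a STAT Total Protein will be performed as a condition of initiating plasmapheresis at subsequent collection visits". Hematocrit is checked before every donation.
- **Sections 5.7 and 8.1** present SPEP as a donor-safety measure for everyone undergoing plasmapheresis, whatever the cohort or arm. Any abnormality leads to physician referral, early withdrawal and replacement.
- **Table 9, footnote G** says only that SPEP is done at each session. It gives no specimen and no timing relative to the donation.

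For a repeat collection in Cohort 2, Arm 4, section 5.7 says "serum protein electrophoresis (SPEP) and STAT total protein will be performed just prior to the subsequent plasmapheresis", and section 8.1.2 adds that "SPEP and STAT Total Protein will both be performed at any subsequent collection visits as a condition of initiating plasmapheresis".

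**The concern.** Footnote L and section 8.1.3 are both current text, and no other passage reconciles them. A specimen taken from the donation exists only once collection is under way. It cannot tell staff, before they start, that the subject should not donate that day.

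What is at stake is a donor-safety step in healthy volunteers in the cohort with the heaviest collection burden: 3 to 4 sessions, as little as 7 days apart. Suppose a new protein abnormality is first detectable at a repeat visit. Under footnote L, the subject would already have given up to 800 mL more plasma before that visit's SPEP could show it. Staff working from the events schedule could follow its footnote in good faith and miss the section 8.1.3 requirement.

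The consequence of a bad result is also unclear. Sections 5.7 and 8.1 end the subject's participation, while section 8.1.3 allows a return visit after at least 7 days.

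**Working it through.** The plan gives no figure for this point, so the check is a comparison of texts followed by a count.

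**Comparison for a repeat Cohort 3 session**

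| Question | Table 8 footnote L | Section 8.1.3 | Arm 4 repeat rule (5.7, 8.1.2) |
|---|---|---|---|
| Specimen | donated plasma | not named | not named; the test is defined as serum electrophoresis |
| Timing | at the visit, and necessarily after collection begins | immediately before the donation | immediately before the donation |
| Can the result stop this donation? | no | yes, by its own wording | yes, a condition of starting |

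Following footnote L alone therefore does not satisfy section 8.1.3. The nearest parallel in the protocol, the Arm 4 repeat rule, agrees with section 8.1.3.

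**Sessions per subject**

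Inputs:
- "The total starting volume of plasma needed from each Cohort 3 subject is approximately 1,620 mL" (Synopsis).
- Maximum of 800 mL per collection (section 8.1.3).
- Minimum acceptable collection of 500 mL (sections 5.7 and 8.1.3).
- 8 subjects in Cohort 3.

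Calculation:
- At the maximum volume: 1,620 / 800 = 2.03, so 3 sessions.
- At the minimum volume: 1,620 / 500 = 3.24, so 4 sessions.

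This agrees with Table 8 footnote F, "Cohort 3 will require 3 to 4 plasma donation sessions", and with section 5.7. Section 8.1.3 itself gives 2 to 3 donations. Two donations yield at most 2 × 800 = 1,600 mL, which is 20 mL below the approximate requirement, so 3 to 4 is better supported. Both counts are shown below.

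**Repeat sessions affected** = subjects × (sessions − 1)
- With 3 to 4 sessions: 8 × 2 = 16 to 8 × 3 = 24.
- With 2 to 3 donations: 8 × 1 = 8 to 8 × 2 = 16.

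These counts leave out collections to replace damaged units and collections from replacement subjects. The first session is also left out, because the explicit just-before timing covers only second and later donations.

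**What cannot be computed.** The documents give no SPEP limits, so the number of donations the check would have stopped cannot be estimated. They give no SPEP turnaround time either; only total protein is ordered STAT.

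**The case against.** The best defence is that footnote L is loose wording. Section 5.7 defines SPEP as a serum test, and SAP Listing 31 carries the same name, so a competent site would draw blood and follow the procedure in section 8.1.3. Footnote L is also compatible with sections 5.7 and 8.1, where SPEP is simply done at each collection and an abnormality leads to withdrawal. Section 8.1.2 has the first Arm 4 SPEP measured during the donation, so the protocol does contemplate a SPEP that does not precede collection. For Cohort 3, section 8.1.3 expressly makes only total protein a condition of starting. On that view, amending 8.1.3 would be as coherent as amending the footnote.

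Part of this stands. The count is a ceiling for planned sessions, conditional on the site following the footnote at every repeat visit, and a same-day SPEP result may never have been achievable. The contradiction remains, because section 8.1.3 still refers to eligibility for the current collection and the Arm 4 repeat rule supports that reading.

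Three stronger readings are tempting, and the documents do not support them.

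- **A reader might infer that SPEP monitoring is lost.** It is not. Footnote L still runs the test at every visit, and the previous session's result may be available. Only a SPEP from that visit, before that visit's donation, is missing.
- **A reader might infer that repeat donations would go ahead unchecked.** Total protein, done STAT or within the preceding 24 hours, and hematocrit both still come first.
- **A reader might take the single mark in Tables 8 and 9 as proof that only one SPEP per visit is allowed.** A mark shows that a test occurs, not how often; vital signs carry one mark at an infusion visit and are measured many times. A site could in principle run two SPEPs, but nothing tells it to.

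**Conclusion.** The conflict is real and minor. Followed literally, footnote L cannot do what section 8.1.3 asks at a repeat Cohort 3 collection. On the better-supported session count, up to 16 to 24 planned repeat sessions would start without a SPEP from that visit; on section 8.1.3's own count, 8 to 16. Both ranges assume 8 subjects and a site that takes its specimen instruction from the footnote throughout.

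The disagreement over an abnormal result is part of the same defect. It would be wrong to call the consequence merely permissive on the strength of section 8.1.3, because sections 5.7 and 8.1 make withdrawal and replacement mandatory.

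No endpoint, analysis population, randomization step or FDP versus FFP comparison depends on this. It is a donor-safety and operating-instruction issue.

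**What to change.** 1. Replace Table 8 footnote L with: *SPEP is performed on a blood sample drawn from the subject before each plasmapheresis collection; for the second and later collections the result is reviewed before collection starts.* The second clause is needed because a pre-donation draw with a late result would not restore the check.
2. If same-day results are not feasible, say so in both footnote L and section 8.1.3: each SPEP result must be reviewed before the next session, and STAT total protein governs the current one.
3. Bring the rescheduling sentence in section 8.1.3 into line with the withdrawal rule in sections 5.7 and 8.1.

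The cost is one footnote and one or two sentences in section 8.1.3. At most it adds one small tube at a visit where blood is already taken for hematocrit. Table 9 already allows about 607 − 600 = 7 mL beyond the donation at each collection visit. No analysis or SAP table changes.

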#### 6.6. Measures Taken to Minimize/Avoid Bias

#### 6.6.1. Randomization

Subjects in Cohorts 1 and 2 will not be randomized. The list of WB and plasmapheresis donors who have previously indicated an interest in participating in research will be sorted by donation type. The center will work through the list using a systematic scheme that represents a diverse subset of the population without bias based on race, ethnicity, gender, or age (as determined by the protocol) until target numbers have been reached. Research recruitment flyers are also posted at the blood center. These flyers include a telephone number for donors to call if they are interested in learning about research participation.

Subjects who are recruited and eligible for WB donations in Cohort 1 will be automatically assigned to the FDP-CPD study arm. Similarly, plasmapheresis donors who are enrolled will automatically be assigned to the FDP-ACD study arm of Cohort 1. The same process for assigning subjects to the FDP-CPD and FDP-ACD arms in Cohort 2 will be applied.

For Cohort 3, which includes product crossover of FDP-ACD and FFP, only plasmapheresis donors who consent to the study are potentially eligible for study enrollment. Cohort 3 subjects are randomized no more than 48 hours prior to their first infusion in a 1:1 ratio to one of two treatment arms that will determine the order in which the two plasma treatment products, FFP and FDP-ACD, are to be infused across the two study infusion visits. Based on this, some subjects will receive FDP-ACD at the first infusion visit while others will receive FFP at the first infusion visit. Cohort 3 subjects who leave the study without completing both infusion visits will be replaced; the replacement subject, assigned a unique SID, will be assigned to the same treatment arm as the discontinued subject. The randomization list allows for over-enrollments and additional randomization slots to compensate for subjects who discontinue early. The Westat Statistician is responsible for the randomization assignments performed via the study website [https://www.fdpcollaboration.org]. Fifth floor HBC FDP research staff who randomize and prepare plasma products will complete the FDP-1 Randomization Worksheet, which contains a series of questions to verify subject eligibility. HBC FDP research staff will log on to the website and submit the worksheet information to request randomization. Shortly after the request is submitted, they will receive a confirmation email of the unmasked study arm assignment (including the randomization number). Fifth floor HBC FDP research staff will maintain records and prepare the appropriate plasma product according to the clinical site's SOPs and the study's MOP.

